### **10.1 Follow Up of Grade 3 or 4 Toxicities**

Grade 3 or 4 toxicities are to be followed by re-evaluation every 2 days, as feasible, until the toxicity returns to Grade  $\leq 2$  severity.

### **10.2 Infection Follow Up**

Any new infection that occurs on study regardless of infecting agent (i.e., viral or non-viral) should be captured. Additionally, the site of infection and source of culture (BAL, tracheal aspirate, sputum, blood, urine, etc.) should also be recorded.

### **10.3 Classification of Causality**

Attribution is the relationship between an adverse event or serious adverse event

and the study treatment. Attribution will be assigned as follows:

- Definite – The AE is clearly related to the study treatment.
- Probable – The AE is likely related to the study treatment

PROTOCOL NUMBER: CCB-CRISIS-01  
PROTOCOL VERSION FINAL DATE: 10SEPT2020

Page 41 of 58

- Possible – The AE may be related to the study treatment.
- Unlikely - The AE is doubtfully related to the study treatment.
- Unrelated - The AE is clearly NOT related to the study treatment

#### Guidance for assessing causality:

The Investigator will need to determine whether an AE is considered related to (“caused by”) the study drug rather than some underlying condition, for example, COVID-19.

For the purposes of this study, ‘drug related’ shall mean ‘Definite’, ‘Probable’ and ‘Possible’ relationship to drug as determined by the Investigator.

#### **10.4 Classification of Severity**

The descriptions and grading scales found in the revised NCI CTCAE version 4.03 will be utilized for AE reporting. All appropriate treatment areas should have access to a copy of the criteria. The CTCAE version 4.03. A copy of the CTCAE version 4.03 can be downloaded from the Cancer Therapy Evaluation Program (CTEP) web site [http://ctep.cancer.gov/protocolDevelopment/electronic\\_applications/ctc.htm](http://ctep.cancer.gov/protocolDevelopment/electronic_applications/ctc.htm).

AEs that are expected are subject to expedited reporting only if the adverse event varies in nature, intensity or frequency from the expected toxicity information that is provided in the Investigator Brochure.

#### **10.5 Serious Adverse Event (SAE) Reporting**

The regulatory definition of an SAE is any untoward medical occurrence or effect that at any dose:

- results in death;
- is life threatening (at the time of the event);
- requires in-patient hospitalization or prolongation of existing hospitalization;
- results in persistent or significant disability / incapacity, or
- is a congenital anomaly / birth defect;
- all other events that are considered medically serious by the Investigator.

**Disability** is defined as a substantial disruption of a person’s ability to conduct normal life functions.

**A life-threatening adverse event** is one that places the patient/subject, in the view of the Investigator, at immediate risk of death from the event as it occurred. It does not include an event that, had it occurred in a more severe form, might have caused death.

**An unexpected adverse event** is any adverse drug event, the nature or severity of which is not consistent with the applicable product information (e.g. IB for an unauthorized investigational product or summary of product characteristics for an authorized product).

PROTOCOL NUMBER: CCB-CRISIS-01  
PROTOCOL VERSION FINAL DATE: 10SEPT2020

Page 42 of 58

Enter only one event as the reason for the SAE on the SAE form. Other non-serious events which did not directly result in the SAE should be detailed in the description section on the SAE form and listed separately as AEs if necessary. For fatal SAEs, report the cause of death as an SAE with a fatal outcome rather than reporting death as the SAE term.

Note that hospitalizations for the following reasons should not be reported as SAEs:

- Routine treatment or monitoring of the studied indication, not associated with any deterioration in condition;
- Elective or pre-planned treatment for a pre-existing condition that is unrelated to the indication under study and has not worsened since signing the informed consent;
- Social reasons and respite care in the absence of any deterioration in the subject's general condition;
- Note that treatment on an emergency outpatient basis that does not result in hospital admission and involves an event not fulfilling any of the definitions of an SAE given above is not an SAE.

Death due to disease progression is considered to be an Expected event in patients with severe SARS-CoV-2 infection and does not require reporting on an expedited basis.

**ANY SERIOUS ADVERSE EVENT MUST BE REPORTED IMMEDIATELY (WITHIN 24 HOURS) BY EMAIL TO THE SAE REPORTING EMAIL USING THE FORM PROVIDED. ENTER THE SUBJECT'S AVAILABLE INFORMATION INTO THE ECRF WITHIN 48 HOURS.**

The subjects are to be identified in the immediate and follow-up reports by unique code numbers supplied by the sponsor. The email address for reporting SAEs can be found below and at the front of this protocol.

Reports relating to the subject's subsequent medical course following an SAE must be submitted to the Sponsor contact until the event has subsided or, in case of permanent impairment, it stabilizes, and the overall clinical outcome has been ascertained.

**SAE REPORTING EMAIL:** [contact]

## 10.6 Suspected Unexpected Serious Adverse Reactions (SUSARs)

Suspected, unexpected, serious adverse reactions (SUSARs) are SAEs that are both related to the study drug (Relationship = Related) and unexpected (not previously described in the investigator's brochure). All SUSARs will be reported in an expedited manner to the Sponsor or designee and IRB by the Investigators and to all relevant regulatory authorities by the Sponsor. Expectedness will be judged by the Medical Monitor and site Investigator. It is critical that all SAEs are reported within the 24-hour guideline so that the expectedness determination can be made. SUSARs require immediate attention and expedited reporting to relevant regulatory authorities.

The Sponsor is to ensure that all relevant information about **fatal or life-threatening** SUSARs are appropriately recorded and reported to the concerned Regulatory Authority and to the concerned IRB(s) within seven (7) calendar days of the date of first report to the Medical Monitor/Sponsor. Follow-up information is to be subsequently communicated to the relevant Regulatory Authority within an additional eight calendar days.

All other SUSARs are to be reported to the Regulatory Authority and to the IRB(s) concerned as soon as possible within a maximum of fifteen calendar days of first knowledge by the Medical Monitor/Sponsor.

The Medical Monitor/Sponsor or designee must also inform all Investigators studying the investigational medicinal product about SUSARs and ensure that all IRBs have been notified.

For reported deaths of a subject, the Investigator shall supply the Sponsor and the IRB(s) with requested additional information on an expedited basis.

## 10.7 Pregnancies

Pregnancy occurring in a female subject or a subject's partner during the study period will be documented in the subject's source documents and reported to the Sponsor Contact and to the IRB by the investigational staff within 1 working day of their knowledge of the event. The collection period for a pregnancy occurring in a subject or a subject's partner will begin at the first dose of study drug and will continue through 90 days after the last dose of study drug. Monitoring of the subject or partner should continue until the conclusion of the pregnancy, if the subject or subject's partner has consented to this. Monitoring of the baby should continue for 3 months after birth, if the subject or subject's partner has consented to this.

Pregnancy itself is not an AE; it should be reported for tracking purposes. The Investigator or designee will discontinue the pregnant subject from the treatment aspects of the study, continue to follow her per protocol for safety outcomes only, and advise her to seek prenatal care and counseling from her primary care provider. Data on fetal outcome and breast-feeding will be collected for regulatory reporting and drug safety evaluation.

If the pregnancy is due to a subject's failure to comply with the contraceptive requirements of this protocol, this should also be documented as a protocol deviation.

Complications of pregnancy or congenital abnormalities in the newborn child will be reported appropriately as AEs.

The site clinical staff will request the pregnant subject to notify the site of the outcome of the pregnancy (i.e., birth, loss, or termination). To help ensure this, the site clinical staff will follow-up with the subject until the end of pregnancy, with the subject's consent. This request and the subject's response will be documented in the subject's source document.

### **10.8 Safety Monitoring for Hematologic Toxicities**

Myelosuppression is a known effect of DHODH inhibition that is associated with prolonged exposure and high doses. To reduce the risk of this effect with brequinar in COVID-19 subjects, the extensive brequinar safety database with over 1,000 patients has been evaluated to select a dose level expected to be safe and well tolerated with regard to hematologic toxicity. In addition to enhancing safety by selecting a relatively brief 5-day exposure and a low brequinar dose, all subjects in the clinical trial will initially be hospitalized as in-patients and will be under the care of highly qualified infectious disease, critical care, and associated medical personnel. As is standard of care for moderately to severely ill in-patients, daily samples will be obtained for hematology assessments including complete blood count with full differential (WBC, RBC, hemoglobin, hematocrit, platelet count, absolute neutrophils, absolute lymphocytes, absolute monocytes, absolute eosinophils, and absolute basophils). Any clinically significant out-of-range laboratory values will be assessed by hospital staff in a timely manner and treatment needs addressed as appropriate. Clinically significant out-of-range laboratory results will be reported as adverse events.

In addition to real time assessments by the treating clinical team, the Clear Creek Medical Monitor will assess the available hematology data on a weekly basis to identify any pathologic trends or safety issues. Any apparent increase in the expected rate or severity of hematologic safety events will be discussed with the Principal Investigators, the Sponsor, and the Medical Monitor. In addition, the Data Safety Monitoring Board will assess available hematology data on a periodic basis to independently assess any pathologic trends or safety issues. If the rate or severity of hematologic toxicities appears to be above the expected rate or the severity appears worse than that expected, the trial enrollment will be suspended and no further subjects will be treated while a comprehensive data review is conducted. Depending on the outcome of the safety review the study may be stopped, the design adjusted, or the study may continue as designed. Individual and study stopping rules are provided in [Section 8.4](#).

Subjects who are discharged from the hospital before Day 7 will have follow up contacts with study staff (phone calls or other digital media) on Days 7, 15 and 29. Early discharge subjects in the brequinar treatment group will also have samples for safety labs (hematology and chemistry) obtained either at the research facility or at an outpatient laboratory on Study Days  $7 \pm 2$  and  $15 \pm 2$ . The safety laboratory results are to be initially assessed in real time by the Principal Investigator or designated person and the Medical Monitor. Any study drug-related clinically significant out-of-range laboratories or study drug-related adverse events will be followed as needed until resolution or stable.

The in-hospital assessments and phone call visits will specifically ask about possible hematologic toxicity including any evidence of the list below. Early discharge subjects will be provided with a list of the following events in lay terms and will be instructed to call the research team if any of these events occur.

PROTOCOL NUMBER: CCB-CRISIS-01  
PROTOCOL VERSION FINAL DATE: 10SEPT2020

Page 45 of 58

- Ecchymosis/purpura/petechiae
- Epistaxis
- Hemoptysis
- Hematuria
- Gingival bleeding
- Prolonged bleeding time from needle sticks, abrasions or lacerations
- Hematemesis
- Rectal bleeding
- Blood in stool
- Any other unusual bleeding noted by the subject or caregiver

Any of these symptoms considered clinically significant will be recorded as an adverse event and must be followed until resolved or stable.

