### Days 1 - 7 (8 AM ± 8 hours)

- If Day 1 is different date from Screening, confirm subject continues to meet all inclusion and no exclusion criteria.
- Randomize the subject (record date and time of randomization).
- Review Progress Notes and medication records to collect any new or changes to ongoing adverse events or new or changed concomitant medications since previous visit (may be omitted on Day 1 if Screening visit was conducted on same day as Study Day 1). Repeat daily until discharge.
- Collect SOC hematology/chemistry results from the EHR beginning on Day 1 (pre-dose) (may be omitted for Day 1 if Screening visit conducted on same date as Study Day 1) then daily through Day 7 or until the clinician decides daily testing is no longer necessary. Ensure that Day 1 samples are obtained prior to first dose of study drug, if applicable.
- Days 1 (pre-dose), 3, 5, 7:
  - Collect NEWS2 Assessments from the EHR.
  - Collect results for inflammatory markers from EHR for those analyzed locally; collect, process and ship samples for DHO/brequinar PK and cytokine panel to be analyzed at the central laboratory per the Laboratory Manual.
  - Collect and process SARS-CoV-2 nasopharyngeal viral load samples.
  - Record hospitalization status (hospitalized, hospitalized in ICU, discharged) (Day 1 already recorded as part of Inclusion criteria, do not record again).
- Dispense study medication (Days 1 through 5 if in brequinar group) and record date and time of brequinar administration. Keep the drug administration interval as close as possible

PROTOCOL NUMBER: CCB-CRISIS-01  
PROTOCOL VERSION DATE: 06JULY2020 FINAL

Page 38 of 59

to 24 hours. Ensure Day 1 labs are drawn prior to first brequinar dose on Day 1. If a subject taking brequinar is discharged prior to Day 5, administer final dose on day of discharge. Do not give subject study drug to take home.

- Drug accountability Day 7  $\pm$  2 days.

**Final Visit Day 15** (8 AM  $\pm$  2 days) or Hospital Discharge Day if earlier than Day 15

- Review Progress Notes and the medication record to collect information for any adverse events or new concomitant medications since Day 7 (from EHR if subject still hospitalized, otherwise by phone or other digital media).
- Collect results for SOC hematology/chemistry from the EHR if subject still hospitalized.

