#### **Subjects in the Brequinar Treatment Group**

If the subject is in the brequinar treatment group and is being discharged prior to completing the study, ensure a hematology/chemistry sample is obtained prior to discharge on the day of discharge. The subject is to return to the research or out-patient facility for the Days 7 and 15 visits if able and permitted. If unable or not permitted to return to the research facility due to COVID-19 restrictions, the remaining visit activities except for the lab draw will be conducted by phone

PROTOCOL NUMBER: CCB-CRISIS-01  
PROTOCOL VERSION FINAL DATE: 10SEPT2020

Page 22 of 58

or other digital media. The lab draw will be performed by an outpatient laboratory at a designated facility. Lab draws for any outpatient visits for the Day 7 and 15 visits are limited to safety labs (hematology and chemistry). Additional outpatient laboratory or study visits are to be conducted as needed for follow up of adverse events including hematologic toxicities.

PROTOCOL NUMBER: CCB-CRISIS-01  
PROTOCOL VERSION FINAL DATE: 10SEPT2020

Page 23 of 58

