## 8 STUDY TREATMENTS

### 8.1 Description of Study Medications

#### 8.1.1 Brequinar

Brequinar will be supplied as 100 mg capsules. Dosing will be a single 5-day course of brequinar 100 mg once daily for 5 doses. The initial brequinar dose (Day 1) should be administered as soon as possible based on study drug availability from the investigational pharmacy. At least the first dose of study medication is to be taken in the hospital. Subjects in the brequinar group discharged before Day 5 will be dispensed brequinar to take at home daily until all 5 doses have been taken.

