#### 8.4.2 Study-Level Stopping Criteria

Following assessment by the Data Safety Monitoring Board (DSMB, see [Section 10.9](#)), the study is to be stopped as shown below:

- If  $\geq 4$  subjects on the brequinar treatment arm develop the same Grade 3 or 4 adverse event or symptomatic laboratory abnormality
- If  $\geq 8$  subjects on the brequinar treatment arm develop any Grade 3 or 4 adverse event or symptomatic laboratory abnormality.

### 8.5 Hospital Discharge Prior to Study Day 15

Subjects discharged from the hospital prior to the Day 15 visit are to return to a research facility when feasible for the remaining study visits. All scheduled study assessments are to be completed at these visits when conducted at a research facility.

PROTOCOL NUMBER: CCB-CRISIS-01  
PROTOCOL VERSION FINAL DATE: 10SEPT2020

Page 30 of 58

For subjects in the brequinar treatment group discharged from the hospital prior to Day 5, the subject is to take home the remaining doses of brequinar for daily self-administration. All subjects (brequinar and SOC) should have the scheduled assessments, e.g. lab samples and the nasopharyngeal swab, on the day of discharge and enter these results on the appropriate EDC page. Following discharge, subjects are to return to the research or out-patient lab collection facility for the remaining study visits, if feasible. Out-patient lab results are to be entered into the EDC and reviewed by a member of the study team. It is important that every effort be made to have subjects return at least on Days 7 and 15, if feasible. Subjects in the brequinar group are to record brequinar dosing on the medication diary provided by the study team. The study team will arrange for the subject to return any unused study medication to the research facility.

For all subjects, if discharge occurs on Days 10, 11, or 12, ensure a hematology/chemistry sample has been obtained on the day of discharge and record these results on the appropriate EDC page. Following discharge, the subject is to return to the research or out-patient lab collection facility for the Day 15 visit, if feasible. Out-patient lab results are to be entered into the EDC and reviewed by a member of the study team.

If discharge occurs on Days 13, 14 or 15, complete the Day 15 Final Visit activities prior to discharge. No further visits are required unless follow up is needed for a study drug-related AE or an SAE; the Day 29 mortality assessment is still to take place.

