If the subject is unable or not permitted to return for planned study visits, the visit activities will be conducted by contacting the subject (phone or other digital media) except for the lab draw. The lab draw will be completed at a research facility or an outpatient laboratory, if feasible, and the results entered into the EDC and reviewed by the study team.

Study completion or the reason for study discontinuation will be recorded in the source document and the eCRF. A subject is considered completed the study if they have assessments through Day 15, whether conducted in the hospital or contacted via phone or other digital media.

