### Days 1 - 7 (8 AM ± 8 hours)

- If Day 1 is a different date from Screening, confirm subject continues to meet all inclusion and no exclusion criteria.
- Randomize the subject (record date and time of randomization).
- Review Progress Notes and medication records to collect any new or changes to ongoing adverse events or new or changed concomitant medications since previous visit (may be omitted on Day 1 if Screening visit was conducted on same day as Study Day 1). Repeat daily until discharge.
- Collect SOC hematology/chemistry results from the EHR beginning on Day 1 (pre-dose) (may be omitted for Day 1 if Screening visit conducted on same date as Study Day 1) then daily through Day 7 or until the clinician decides daily testing is no longer necessary. Ensure that Day 1 samples are obtained prior to first dose of study drug, if applicable.
- Days 1 (pre-dose), 3, 5, 7:
  - Collect NEWS2 Assessments from the EHR.
  - Collect results for inflammatory markers from EHR for those analyzed locally; collect, process and ship samples for DHO/brequinar PK and cytokine panel to be analyzed at the central laboratory per the Laboratory Manual.
  - Collect and process SARS-CoV-2 nasopharyngeal viral load samples.
  - Record hospitalization status (hospitalized, hospitalized in ICU, discharged) (Day 1 already recorded as part of Inclusion criteria, do not record again).
- Dispense study medication (Days 1 through 5 if in brequinar group) and record date and time of brequinar administration. Keep the drug administration interval as close as possible

PROTOCOL NUMBER: CCB-CRISIS-01  
PROTOCOL VERSION FINAL DATE: 10SEPT2020

Page 37 of 58

to 24 hours. Ensure Day 1 labs are drawn prior to first brequinar dose on Day 1. If a subject taking brequinar is discharged prior to Day 5, give the subject adequate study drug to take home along with a diary to record daily treatment administration through Day 5.

- Drug accountability Day 7  $\pm$  2 days.

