### **9.6 Compliance with Study Procedures**

The time at which study procedures are conducted should follow the protocol timelines as closely as possible. However, it is recognized in a clinical setting that protocol-specified timings may not occur exactly as specified in the protocol. Provided that activities are carried out within the identified windows it will not be necessary to file a protocol deviation. It is understood that some scheduled study assessments may not be able to be conducted if the subject is unable to return to the clinic after discharge due to COVID-19 restricted travel; it is also understood that crowded hospital conditions/lack of personnel may make it impossible to carry out all requested study procedures; this will not be counted as a protocol deviation. The Day 7 and 15 visits are to be conducted via telephone if the subject has been discharged from the hospital with lab draws for subjects in the brequinar treatment group as described in [Section 8.5](#).

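### Section 10.8 still fixes post-discharge staff contacts at Days 7, 15 and 29, a schedule set when take-home drug was forbidden, although early-discharged brequinar subjects may now take 1 to 4 of 5 doses at home

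*Protocol*

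**What the plan says.** Home dosing. Section 8.1.1 requires at least the first dose in hospital and says that brequinar subjects "discharged before Day 5 will be dispensed brequinar to take at home daily until all 5 doses have been taken". Section 9.5 tells sites to "give the subject adequate study drug to take home along with a diary to record daily treatment administration through Day 5".

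Contacts after discharge. Section 10.8 says that subjects discharged before Day 7 "will have follow up contacts with study staff (phone calls or other digital media) on Days 7, 15 and 29", with safety labs for the brequinar arm on Days 7 ± 2 and 15 ± 2. Section 9.6 says "The Day 7 and 15 visits are to be conducted via telephone if the subject has been discharged from the hospital", and that sentence ends by referring to 8.5 for the brequinar lab draws. Section 3.9 says "The subject is to return to the research or out-patient facility for the Days 7 and 15 visits if able and permitted".

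Section 8.5 is wider. It sends discharged subjects to all remaining study visits if feasible and adds: "It is important that every effort be made to have subjects return at least on Days 7 and 15, if feasible". For subjects who cannot return, "the visit activities will be conducted by contacting the subject (phone or other digital media) except for the lab draw". Section 8.2.1 has safety assessed at every study visit.

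The AE review in 9.5 and the AE row of Appendix A are daily, but only up to discharge. Section 8.4.1 stops study drug permanently for a related Grade 3, or any Grade 4, symptomatic toxicity. The only instruction in this protocol for discharged subjects to phone the team is the list of bleeding events in 10.8.

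The contact days in 10.8 and 9.6 read the same in the 06JULY2020 version, whose Section 9.5 said "Do not give subject study drug to take home". That version is cited only to show where the schedule comes from.

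**The concern.** While dosing ended at discharge, a first contact on Day 7 was reasonable: no treatment decision remained. Once up to four doses are taken at home, stopping treatment under 8.4.1 depends on staff asking or on the subject reporting. A site that works from 10.8, the safety monitoring section, would first ask about AEs two days after the last scheduled dose. The subject has been told to phone about bleeding. Nausea, vomiting, diarrhea, stomatitis and rash, which 8.2.1 lists among the common brequinar effects, have no stated prompt.

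Safety and tolerability is the primary objective. What is at stake is late application of the individual stopping rule, and AE inquiry that differs between sites according to which section they follow.

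**Working it through.** The plan gives no figure to reproduce here, so the check is a count and a comparison of sections.

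**Inputs.** Five daily doses, the last on Day 5 (8.1.1, 9.5); at least one in hospital (8.1.1); dosing interval 24 h ± 6 h (8.2); scheduled visit days 3, 5, 7 and 15 (9.5, Appendix A); contacts named in 10.8 on Days 7, 15 and 29.

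**Home doses after discharge on Day k.** If that day's dose is given first, 5 − k. If not, 6 − k, which excludes k = 1 because the first dose is taken in hospital.

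**Contacts on home-dosing days.** Under 10.8 there are none. Under 8.5, read to include Days 3 and 5, the number is the count of those two days falling after k.

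**Days from discharge to first contact.** Under 10.8, 7 − k. Under 8.5, 3 − k for k = 1 or 2, and 5 − k for k = 3 or 4.

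| Discharge day k | Home doses (day's dose given / not given) | Contacts while dosing: 10.8 / 8.5 | Days to first contact: 10.8 / 8.5 |
|---|---|---|---|
| 1 | 4 / – | 0 / 2 | 6 / 2 |
| 2 | 3 / 4 | 0 / 2 | 5 / 1 |
| 3 | 2 / 3 | 0 / 1 | 4 / 2 |
| 4 | 1 / 2 | 0 / 1 | 3 / 1 |

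**Does Day 7 always follow the last dose?** With every interval at 24 + 6 = 30 h, dose 5 comes 4 × 30 = 120 h after dose 1. Dose 1 falls no later than hour 24, so dose 5 falls no later than hour 144, the start of Day 7. The Day 7 contact therefore comes after dosing even at the limit of the interval. The Day 7 ± 2 safety lab is different: it can fall as early as Day 5, the last dosing day.

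**What 8.5 settles and what it leaves open.** Days 3 and 5 are scheduled visits, 8.5 covers remaining visits in person or by phone, and 8.2.1 attaches safety assessment to each visit. Together these support contacts on Days 3 and 5. But 8.5 names only Days 7 and 15, lists no AE inquiry, and sits beside an AE review that ends at discharge in 9.5 and Appendix A. A site can follow 10.8 as written and make no contact during home dosing, or follow 8.5 and make one or two.

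**Prior safety rate.** Section 8.2.1 reports related Grade 3 or 4 AEs in 2 of 39 subjects given five daily IV doses at or below 100 mg: 2/39 = 5.1%, exact 95% CI 0.6% to 17.3%. Applied to 16 brequinar subjects this is 16 × 0.051 = 0.8 (0.1 to 2.8). The two events were hyperbilirubinemia and hyperglycemia, which laboratory tests find and calls would not. The rate therefore does not measure what the missing contacts would catch.

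**The case against.** The best defence is that 8.5 governs. Sections 5 and 9.5 and Appendix A all refer to it for early discharge, and the 9.6 sentence itself points there for lab draws. Section 8.5 covers the remaining visits by phone where needed, and nothing in 10.8, 9.6 or 3.9 says that its days are the only ones. Section 3.9 also allows extra visits as needed for AEs, and Section 10 has subjects questioned about AEs. The amendment that introduced home dosing wrote the new 8.5 text with Days 7 and 15 as the minimum for return, and edited 3.9 while keeping those days, so the days may be partly a deliberate choice.

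Much of this stands. A reader might infer that the protocol provides no contact at all before Day 7; 8.5 does not support that. Nor would it be right to say that missed inquiries are excused: the Appendix A clause on deviations covers items missed when a phone visit occurs, and so presupposes the call. Nor are events lost, since AEs are collected through Day 15.

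What the defence does not remove is the mismatch. Contact on Days 3 and 5 has to be inferred from several sections, while the section titled for hematologic safety monitoring states a different schedule outright.

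**Conclusion.** The point holds as an inconsistency between sections with a practical safety consequence. Under 10.8 alone, no staff AE inquiry falls within home dosing for any discharge day from 1 to 4, and the 8.4.1 rule for symptomatic toxicity may not be applied before the last dose. Under 8.5, read with 8.2.1, one or two contacts would occur.

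The size is limited. The protocol gives no early-discharge rate, so the number affected is unknown and could be zero. Absolute risk looks low: Section 3.7 ties the dose-limiting effects to higher IV doses and longer courses, and none of the 39 earlier subjects discontinued for a related AE. The 5.1% rate should not be read as a count of events that would be missed. The consequence is late detection and uneven inquiry between sites.

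The conclusion assumes that some sites would work from 10.8, and that dosing keeps to the stated interval. The subject information sheet and medication diary are not shown and may carry a broader call-in instruction. Severity: minor to should-fix.

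**What to change.** In 10.8, with matching lines in 8.5, 9.6 and Appendix A, state a phone or digital AE contact on Days 3 and 5 for every subject already discharged. Apply it in both arms so that ascertainment stays comparable, and add diary dose confirmation for brequinar subjects. Extend the call-in instruction for subjects dosing at home from bleeding to any severe symptom, to be reported before the next dose is taken.

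The cost is wording plus at most two short calls per early-discharged subject, or one if discharge is on Day 3 or 4. The ceiling is 2 × 24 = 48 calls if all 24 subjects left by Day 2. Sites that already read 8.5 as covering Days 3 and 5 add none. The phone route and the diary exist, and no extra visit or laboratory test is needed.
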